- MAAEs from Day 1 through Day 394 (Part A) and OL-Month 6 or 7 (Part B and Part C) or withdrawal from the study.
- SAEs from Day 1 through Day 394 (Part A) and OL-Month 6 or 7 (Part B and Part C) or withdrawal from the study.
- Results of safety laboratory tests (Part A).
- Vital sign measurements (Part A, Part B, and Part C).
- Physical examination findings (Part A, Part B, and Part C).
- Assessments for SARS-CoV-2 infection from Day 1 through study completion (Part A, Part B, and Part C).

Immunogenicity Assessments:

Immunogenicity assessments will include the following in Part A and Part B:

- Serum bAb level against SARS-CoV-2 as measured by enzyme-linked immunosorbent assay (ELISA) specific to the SARS-CoV-2 spike protein
- Serum nAb titer against SARS-CoV-2 as measured by pseudovirus and/or live virus neutralization assays

In Part C, serum samples for immunogenicity assessment will be analyzed for:

- Serum nAb against SARS-CoV-2 as measured by pseudovirus (and/or live virus) using the B.1.351 and the D614G variant sequences of SARS-CoV-2 S protein (and/or variant strains)
- Serum bAb against SARS-CoV-2 as measured by ELISA against the B.1.351 and the D614G variant sequences of SARS-CoV-2 S protein

Investigational Product, Dosage, and Route of Administration:

mRNA-1273 vaccine, dosed in Part A and Part B, is a lipid nanoparticle (LNP) dispersion of an mRNA encoding the prefusion stabilized S protein of SARS-CoV-2 formulated in LNPs composed of 4 lipids (1 proprietary and 3 commercially available). The mRNA-1273 vaccine is provided as a sterile liquid for injection, white to off white dispersion in appearance, at a concentration of 0.5 mg/mL in 20 mM Tris buffer containing 87 mg/mL sucrose and 10.7 mM sodium acetate at pH 7.5.

The mRNA-1273 vaccine dosed in Part C is provided at a concentration of 0.2 mg/mL in 20 mM Tris buffer containing 87 mg/mL sucrose and 4.3 mM sodium acetate at pH 7.5.

mRNA-1273.351 vaccine, dosed in Part C, is a LNP dispersion, with an mRNA encoding the prefusion stabilized S protein of SARS-CoV-2 variant B1.351. The mRNA is formulated in LNPs composed of 4 lipids (1 proprietary and 3 commercially available). The mRNA-1273.351 vaccine in Part C is in 20 mM Tris buffer containing 10.7 mM of sodium acetate at pH 7.5 and provided at a concentration of 0.5 mg/mL. mRNA-1273 and mRNA-1273.351 vaccines will be mixed at the clinical site to enable dosing of the mRNA-1273/mRNA-1273.351 (50 µg total) arm.

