In Part A, the investigational product will be prepared for injection as a single 0.5 mL dose for each participant based on the cohort and randomization assignment, as detailed in the mRNA-1273-P201 Pharmacy Manual. In Part B, the investigational product will be prepared for injection as a single 0.5 mL dose volumes for each participant as detailed in the mRNA-1273-P201 Pharmacy Manual. In Part C, the investigational product will be prepared for injection as a single dose with varied volumes for each participant as detailed in mRNA1273-P201 Pharmacy Manual addendum for Part C. Unblinded pharmacy personnel, who will not participate in any other aspect of the study during Part A, the Blinded Phase, will perform investigational product accountability, dose preparation, and investigational product administration. The investigator will designate an unblinded clinical team member to provide oversight to the administration of investigational product so that it proceeds according to the procedures stipulated in this study protocol and the mRNA-1273-P201 Pharmacy Manual. Study-specific training will be provided.

At each visit when investigational product is administered, participants will be monitored for a minimum of 30 minutes after administration. Assessments will include vital sign measurements and monitoring for local or systemic reactions (Schedule of Events, [Table 9](#)).

Eligibility for subsequent investigational product injection is determined by following the criteria outlined in [Section 3.3.2.2](#).

The study site will be appropriately staffed, staff will be trained on emergency resuscitation, and will have stocked rescue medications (such as epinephrine, steroids, antihistamines, and intravenous fluids) should any severe reaction (eg, anaphylaxis or urticaria) occur that requires immediate intervention.

The rules for pausing dosing are provided in [Section 3.3.2.1](#).

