3.3.3 Identity of Investigational Product

The mRNA-1273 vaccine dosed in Part A and Part B of this study is an LNP dispersion of an mRNA encoding the prefusion stabilized S protein of SARS-CoV-2. The mRNA-1273.351 vaccine dosed in Part C of this study is an LNP dispersion of an mRNA encoding the prefusion stabilized S protein of SARS-CoV-2 variant B1.351. The mRNA-1273/mRNA-1273.351 mixture vaccine dosed in Part C of this study utilizes a mixture of mRNA-1273 and mRNA-1273.351 drug products to administer a single dose containing both vaccines. All vaccines are formulated in LNPs composed of 4 lipids (1 proprietary and 3 commercially available): the proprietary ionizable lipid SM-102; cholesterol; 1,2-distearoyl-sn-glycero-3-phosphocholine (DSPC); and 1-monomethoxypolyethyleneglycol-2,3-dimyristylglycerol with polyethylene glycol of average molecular weight 2000 (PEG2000-DMG).

The mRNA-1273, mRNA-1273.351, and mRNA-1273/mRNA-1273.351 mixture vaccines are provided as sterile liquids for injection, white to off white dispersion in appearance. The mRNA-1273 vaccine dosed in Part A and Part B is in 20 mM Tris buffer containing 87 mg/mL sucrose and 10.7 mM sodium acetate at pH 7.5 and is provided at a concentration of 0.5 mg/mL. The mRNA-1273 vaccine dosed in Part C is in 20 mM Tris buffer containing 4.3 mM of sodium acetate at pH 7.5 and is provided at a concentration of 0.5 mg/mL. The mRNA-1273.351 vaccine in Part C is in 20 mM Tris buffer containing 10.7 mM of sodium acetate at pH 7.5 and provided at a concentration of 0.2 mg/mL. mRNA-1273 and mRNA-1273.351 vaccines will be mixed at the clinical site to enable dosing of the mRNA-1273/mRNA-1273.351 (50 μg total) arm.

The placebo is 0.9% sodium chloride (normal saline) injection, USP.

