3.3.4 Management of Investigational Product

3.3.4.1 Delivery and Receipt

The Sponsor or designee is responsible for the following:

- Supplying the investigational product
- Confirming the appropriate labeling of mRNA-1273, mRNA-1273.351, and mRNA-1273/mRNA-1273.351 mixture Injection, so that it complies with the legal requirements of the US

The investigator is responsible for acknowledging the receipt of the investigational product by a designated staff member at the site, including the following:

- Confirming that the investigational product was received in good condition
- Confirming that the temperature during shipment from the Sponsor to the investigator's designated storage location was appropriate
- Confirming whether the Sponsor has authorized the investigational product for use
- Ensuring the appropriate dose level of mRNA-1273, mRNA-1273.351, and mRNA-1273/mRNA-1273.351 mixture Injection is properly prepared using aseptic technique

Further description of the investigational product and instructions for the receipt, storage, preparation, administration, accountability, and destruction of the investigational product are described in the mRNA-1273-P201 Pharmacy Manual addendum for Part C.

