3.3.4.2 Packaging and Labeling

The Sponsor will provide the investigator and study site with adequate quantities of mRNA-1273, mRNA-1273.351, and mRNA-1273/mRNA-1273.351 mixture. The sterile vaccine product used in Part A and Part B is packaged in a 2-mL glass vial with a 0.6-mL fill volume. The mRNA-1273 vaccine used in Part C is packaged in a 10-mL vial with a 6.3-mL fill volume. The mRNA-1273.351 vaccine used in Part C is packaged in a 2-mL vial with a 0.8-mL fill volume. The vaccines will have all required labeling per regulations and will be supplied to the pharmacy in an unblinded manner. Each vial will be individually labeled for future participant identification purposes.

The mRNA-1273 and mRNA-1273.351 injections will be packaged and labeled in accordance with the standard operating procedures (SOPs) of the Sponsor or of its designee, Code of Federal Regulations Title 21 (CFR), Good Manufacturing Practice (GMP) guidelines, International

Council for Harmonisation (ICH) Good Clinical Practice (GCP) guidelines, guidelines for Quality System Regulations, and applicable regulations.

The Sponsor or Sponsor's designee will supply the 0.9% sodium chloride injection for use as both a placebo and a diluent to mRNA-1273 and mRNA-1273.351. The 0.9% sodium chloride bears a commercial label and does not contain study-specific identification.

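### The Synopsis and Section 3.3.3 give exchanged stock concentrations (0.2 and 0.5 mg/mL) for the two Part C vaccines; one is wrong, probably Section 3.3.3

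*Protocol*

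**What the plan says.** The Protocol states the strengths of the two Part C products in two places.

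- **Synopsis, Investigational Product, Dosage, and Route of Administration.** For mRNA-1273: "The mRNA-1273 vaccine dosed in Part C is provided at a concentration of 0.2 mg/mL in 20 mM Tris buffer", with 4.3 mM sodium acetate. For mRNA-1273.351: "10.7 mM of sodium acetate at pH 7.5 and provided at a concentration of 0.5 mg/mL".
- **Section 3.3.3, Identity of Investigational Product.** For mRNA-1273: "4.3 mM of sodium acetate at pH 7.5 and is provided at a concentration of 0.5 mg/mL". For mRNA-1273.351: "10.7 mM of sodium acetate at pH 7.5 and provided at a concentration of 0.2 mg/mL".

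Both places also say that the two vaccines are combined at the study site for the mixture arm. Section 3.3.4.2 supplies saline "for use as both a placebo and a diluent to mRNA-1273 and mRNA-1273.351".

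Section 3.3.2 gives injected volumes only: 0.2 mL for 20 µg of mRNA-1273.351, and 0.5 mL for both the 50 µg dose and the mixture. It says the product is prepared "as a single dose with varied volumes for each participant as detailed in mRNA1273-P201 Pharmacy Manual addendum for Part C". Section 3.3.4.1 likewise says that instructions for "preparation, administration, accountability, and destruction of the investigational product are described in the mRNA-1273-P201 Pharmacy Manual addendum for Part C".

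**The concern.** Each product keeps its acetate value in both places, but the two concentrations are exchanged. These are ordinary sentences in the current amendment: they are not amendment history, a broken table or redacted text. No other section states the Part C stock strengths, so nothing in the documents resolves the conflict.

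Stock strength matters because the site dilutes and mixes. It determines how much to draw from each vial, and the Protocol gives two answers that are 2.5-fold apart. Dose level and composition are what distinguish the three Part C arms, so a preparation error would mislabel the arms as well as misdose participants. Part C also has fewer automatic safeguards than Part A. The pause rules do not apply (Section 3.3.2.1), and the Part C SAP (Section 6.7) plans no Safety Monitoring Committee review beyond ad hoc meetings.

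**Working it through.** **1. The statements side by side**

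| Product | Source | mRNA (mg/mL) | Acetate (mM) | Acetate ÷ mRNA |
|---|---|---|---|---|
| mRNA-1273, Parts A/B | Synopsis and 3.3.3 | 0.5 | 10.7 | 10.7/0.5 = 21.4 |
| mRNA-1273, Part C | Synopsis | 0.2 | 4.3 | 4.3/0.2 = 21.5 |
| mRNA-1273.351, Part C | Synopsis | 0.5 | 10.7 | 10.7/0.5 = 21.4 |
| mRNA-1273, Part C | 3.3.3 | 0.5 | 4.3 | 4.3/0.5 = 8.6 |
| mRNA-1273.351, Part C | 3.3.3 | 0.2 | 10.7 | 10.7/0.2 = 53.5 |

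**2. Which statement is likelier to be wrong**

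The Part A/B product is described identically in both places and serves as the reference. Scaling its acetate from 0.5 to 0.2 mg/mL gives 10.7 × 0.2/0.5 = 4.28 mM, which rounds to the 4.3 mM stated for Part C mRNA-1273. The Synopsis pairings fit this scaling and those in Section 3.3.3 do not.

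Presentation points the same way, less strongly. Section 3.3.4.2 says "The mRNA-1273.351 vaccine used in Part C is packaged in a 2-mL vial with a 0.8-mL fill volume", and Section 3.3.4.3 stores that product at -90 to -60°C. The 0.5 mg/mL Part A/B product has the same vial size and storage range. Part C mRNA-1273 comes in a 10-mL vial stored at -25 to -15°C.

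**3. Whether the injected volumes settle it**

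In the single-product arms, 20 µg/0.2 mL = 50 µg/0.5 mL = 0.1 mg/mL. That is a 5-fold dilution from 0.5 mg/mL or a 2-fold dilution from 0.2 mg/mL. In the mixture, 25 µg of each component in 0.5 mL is 0.05 mg/mL, a 10-fold or 4-fold dilution. Both are feasible from either stock, so the volumes do not discriminate.

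**4. Dose delivered if the wrong strength were used**

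Stock volume drawn = intended dose ÷ assumed strength. Dose delivered = volume drawn × true strength.

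| Intended dose | Synopsis true, Section 3.3.3 used | Section 3.3.3 true, Synopsis used |
|---|---|---|
| mRNA-1273.351 20 µg | 0.10 mL × 0.5 mg/mL = 50 µg | 0.04 mL × 0.2 mg/mL = 8 µg |
| mRNA-1273.351 50 µg | 0.25 mL × 0.5 mg/mL = 125 µg | 0.10 mL × 0.2 mg/mL = 20 µg |
| Mixture, mRNA-1273 25 µg | 0.050 mL × 0.2 mg/mL = 10 µg | 0.125 mL × 0.5 mg/mL = 62.5 µg |
| Mixture, mRNA-1273.351 25 µg | 0.125 mL × 0.5 mg/mL = 62.5 µg | 0.050 mL × 0.2 mg/mL = 10 µg |
| Mixture total 50 µg | 72.5 µg (ratio 10:62.5 = 4:25) | 72.5 µg (ratio 25:4) |

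In the first scenario the nominal 20 µg arm would receive the dose intended for the 50 µg arm. The nominal 50 µg arm would exceed 100 µg, the higher of the two Part A dose levels.

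**5. Whether a volume check would catch it in the mixture arm**

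On the Synopsis figures, one 0.5 mL dose takes 0.125 mL mRNA-1273 + 0.050 mL mRNA-1273.351 = 0.175 mL stock. On the Section 3.3.3 figures it takes 0.050 + 0.125 = 0.175 mL. If saline makes up the rest, it is 0.5 − 0.175 = 0.325 mL either way. Neither total stock nor final volume reveals the exchange; only the component volumes do.

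**The case against.** The best counter-argument is that neither statement is a preparation instruction. Sites are directed to the Part C Pharmacy Manual addendum, and there are further controls. Vials carry required labelling (Section 3.3.4.2), and the investigator must ensure that the right dose level is prepared (Section 3.3.4.1). An unblinded team member oversees administration after study-specific training (Section 3.3.2), and an unblinded monitor reviews the accountability log (Section 3.3.4.4). Misdosing would require the wrong figure to be used and every such control to miss it. This stands as a limit on the risk. It does not remove the risk: the documents do not say what strength the label or addendum shows, and Section 3.3.2 names the Protocol alongside the Pharmacy Manual as the standard for administration.

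The direction of the error can also be questioned. No document says that acetate scales with mRNA content, and vial size and storage temperature do not determine concentration. That is fair: the contradiction is certain and the direction is inferred, although agreement at 21.4 to 21.5 across three products is hard to put down to chance.

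The volume-check point is confined to the mixture arm and assumes that saline makes up the remainder. In the single-product arms the stock volumes differ visibly (0.10 versus 0.25 mL for 50 µg), and a worksheet of component volumes with the correct figures would expose the error in the mixture arm too.

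Finally, no calculation in the plan is wrong and no analysis method uses stock concentration. Both are true, but they bear on how the point is classified and not on whether the text needs correcting.

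**Conclusion.** The concern holds. The current Protocol gives two incompatible strengths, 2.5-fold apart, for each Part C vaccine. At least one of the two statements must be wrong. On the assumption that acetate scales with mRNA concentration, it is Section 3.3.3.

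The dose consequences are conditional on the wrong figure having reached preparation, either through the addendum or because a site worked from the Protocol. About 60 participants (20 per arm) are planned; none is shown to have been misdosed. Part C is descriptive and tests no hypothesis (Protocol Section 4.2; Part C SAP Section 4.2), so what is at stake is dose accuracy and correct arm labels. This should be fixed: it is an unambiguous error in a figure that determines dose, with harm that is possible but not demonstrated.

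**What to change.** 1. Confirm both Part C stock strengths against the product release documents.
2. Correct the wrong text, probably Section 3.3.3, so that the Synopsis and Section 3.3.3 state one concentration per product.
3. Confirm that the Part C Pharmacy Manual addendum carries the correct figures.
4. For any Part C doses already given, check the preparation records before dose-group summaries are reported. In the mixture arm, check the volume drawn of each component, because the totals are uninformative. A correct addendum makes this check less pressing but does not replace it, since a site may have worked from the Protocol.

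The cost is a one-line Protocol correction, a check of the addendum, and a review of preparation records for at most about 60 planned participants. No analysis method changes.

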All safety analyses will be based on the Safety Set, except summaries of solicited ARs, which will be based on the Solicited Safety Set. All safety analyses for Part A and Part B will be provided by age cohort unless otherwise specified.

The number and percentage of participants with any solicited local AR, with any solicited systemic AR, and with any solicited AR during the 7-day follow-up period after each injection will be summarized. A 2-sided 95% exact confidence interval (CI) using the Clopper-Pearson method will be provided for the percentage of participants with any solicited AR.

Number and percentage of participants with unsolicited AEs, SAEs, MAAEs, Grade 3 or higher AEs, and AEs leading to discontinuation from study vaccine or participation in the study will be summarized.

Number of events of solicited ARs, unsolicited AEs/SAEs, and MAAEs will be reported in summarization tables accordingly.

For all other safety parameters, descriptive summary statistics will be provided.

For treatment-emergent safety laboratory tests results, the raw values and change from baseline values will be summarized by age cohort (for Part A and Part B), treatment group, and visit at each timepoint.

The number and percentage of participants who have chemistry, hematology, coagulation, and vital signs results below or above the laboratory normal ranges will be tabulated by timepoint.

Demographic variables (eg, age, height, weight, and body mass index (BMI) and baseline characteristics will be summarized by treatment group for each age cohort (when appropriate) by descriptive statistics (mean, standard deviation for continuous variables, and number and percentage for categorical variables).

Data from Part C will be analyzed similarly.

Immunogenicity: The analyses of immunogenicity will be based on the Per-Protocol (PP) Set. For each age cohort (for Part A and Part B), if the number of participants in the Full Analysis Set (FAS) and PP Set differ (defined as the difference divided by the total number of participants in the PP Set) by more than 10%, supportive analyses of immunogenicity may be conducted using the FAS.

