4.6.2 Safety Analyses

Safety and reactogenicity will be assessed by clinical review of all relevant parameters including solicited ARs (local and systemic events), unsolicited AEs, SAEs, MAAEs, AEs leading to discontinuation, safety laboratory test results (Part A only), vital signs, and physical examination findings.

Solicited ARs and unsolicited AEs will be coded by system organ class and preferred term according to the MedDRA for adverse reaction terminology. The Toxicity Grading Scale for Healthy Adult and Adolescent Volunteers Enrolled in Preventive Vaccine Clinical Trials ([DHHS 2007](#)) is used in this study with modification for rash, solicited ARs, and vital signs ([Table 6](#)).

Rash will be graded as:

- Grade 0 = no rash
- Grade 1 = localized without associated symptoms
- Grade 2 = maculopapular rash covering < 50% body surface area
- Grade 3 = urticarial rash covering > 50% body surface area
- Grade 4 = generalized exfoliative, ulcerative, or bullous dermatitis

All safety analyses will be based on the Safety Set, except summaries of solicited ARs which will be based on the Solicited Safety Set. All safety analyses will be provided by age cohort (for Part A and Part B) unless otherwise specified.

The number and percentage of participants with any solicited local AR, with any solicited systemic AR, and with any solicited AR during the 7-day follow-up period after each injection will be summarized. A 2-sided 95% exact CI using the Clopper-Pearson method will be provided for the percentage of participants with any solicited AR.

Number and percentage of participants with unsolicited AEs, SAEs, MAAEs, Grade 3 or higher AEs, and AEs leading to discontinuation from study vaccine or participation in the study will be summarized.

Number of events of solicited ARs, unsolicited AEs/SAEs, and MAAEs will be reported in summarization tables accordingly.

For all other safety parameters, descriptive summary statistics will be provided. [Table 8](#) summarizes the analysis strategy for safety parameters.

Table 8: Analysis Strategy for Safety Parameters

Safety Endpoint	Number and Percentage of Participants, Number of Events	95% CI
Any Solicited AR (overall and by local, systemic)	X	X
Any Unsolicited AE	X	
Any SAE	X	
Any Unsolicited MAAE	X	
Any Unsolicited Treatment-Related AE	X	
Any Treatment-Related SAE	X	
Discontinuation due to AE	X	
Any Grade 3 and above AE	X	
Any Treatment-Related Grade 3 and above AE	X	

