Eosinophils (cell/mm ³)	650 – 1,500	1,501 – 5,000	> 5,000	Hypereosinophilic
Platelets decreased (cell/mm ³)	125,000 – 140,000	100,000 – 124,000	25,000 – 99,000	< 25,000
PT; increase by factor	> 1.0 – 1.10 × ULN	1.11 – 1.20 × ULN	1.21 – 1.25 × ULN	> 1.25 × ULN
PTT; increase by factor	> 1.0 – 1.2 × ULN	1.21 – 1.4 × ULN	1.41 – 1.5 × ULN	> 1.5 × ULN

Abbreviations: PT = prothrombin time; PTT = partial thromboplastin time; ULN = upper limit of normal; WBC = white blood cell.

* The laboratory values provided in the tables serve as guidelines and are dependent upon institutional normal parameters. Institutional normal reference ranges should be provided to demonstrate that they are appropriate. Laboratory abnormality grading occurs only when the values fall beyond the normal ranges established by the local laboratory.

Source: Guidance for industry – Toxicity Grading Scale for Healthy Adult and Adolescent Volunteers Enrolled in Preventive Vaccine Clinical Trials; tables for laboratory abnormalities (DHHS 2007). Note that the criteria for Grade 1 PT and PTT have been adjusted from the source table: instead of $\geq 1.0 \times$ ULN, both criteria are $> 1.0 \times$ ULN. Grade 1 will not be used for hematology values due to the large overlap with normal values at the central laboratory.

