PPD Biostatistics and programming team, designee of Moderna Biostatistics and Programming department, will perform the statistical analysis of the safety, reactogenicity, and immunogenicity data; Statistical Analysis System (SAS) Version 9.4 or higher will be used to generate all statistical outputs (tables, figures, listings, and datasets). The SAP will be finalized and approved prior to the primary analysis clinical database lock and treatment unblinding for the study. If the methods in this SAP differ from the methods described in the protocol, the SAP will prevail.

2. Study Objectives

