6.3.1.2. TEAEs by System Organ Class and Preferred Term

The following summary tables of TEAEs will be provided by SOC and PT using frequency counts and percentages (ie, number and percentage of subjects with an event):

- All unsolicited TEAEs
- All unsolicited TEAEs that are treatment-related
- All serious TEAEs
- All serious TEAEs that are treatment-related

- All unsolicited TEAEs leading to discontinuation from participation in the study
- All unsolicited Severe TEAEs
- All unsolicited Severe TEAEs that are treatment-related
- All unsolicited TEAEs that are medically-attended

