6.3.3. Clinical Laboratory Evaluations

Safety laboratory testing will be performed in Part A of the study and will include hematology, serum chemistry, coagulation, and pregnancy test.

A pregnancy test will be performed on all female subjects of childbearing potential at the Screening Visit and before each vaccine administration (Day 1 and Day 29) via point-of-care urine, and as needed at unscheduled visits (urine or serum pregnancy test based on the Investigator's discretion).

All laboratory test results, including screening safety laboratory tests for Cohort 1 and Cohort 2 subjects and post-baseline tests for Cohort 2 subjects, will be presented in the data listings. The results that are outside the reference ranges will be flagged in the data listings. The abnormalities meeting the toxicity grading criteria in any safety laboratory (hematology, serum chemistry and coagulation) will be listed separately. If a subject has an

abnormal laboratory test at any post injection visit, then all results for that subject and laboratory test will be presented in the listing.

For continuous hematology, serum chemistry, and coagulation measurements, the observed values and changes from baseline will be summarized at each visit by vaccination group as defined in [Section 6.1](#) for Cohort 2. The number and percentage who had any abnormal result based on toxicity grades in hematology, serum chemistry, or coagulation measurements will also be summarized by visit and vaccination group for Cohort 2. Shift from baseline in the toxicity grades to the worst post-baseline result in the vaccination stage will also be summarized by vaccination group for Cohort 2.

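### The Part A/B SAP replaces the protocol's out-of-range laboratory count with a toxicity-grade count that has no haematology Grade 1; both SAPs specify no event counts; neither departure is declared

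*Protocol*

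**What the plan says.** **Protocol, laboratory results.** Abnormal safety laboratory results in Cohort 2 at Days 29 and 57 are a primary safety endpoint of Part A (4.3.1.1.1). The synopsis and section 4.6.2 both say that the number and percentage of participants with "chemistry, hematology, coagulation, and vital signs results below or above the laboratory normal ranges will be tabulated by timepoint".

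**Protocol, events.** The synopsis and 4.6.2 state: "Number of events of solicited ARs, unsolicited AEs/SAEs, and MAAEs will be reported in summarization tables accordingly". Table 8 heads its results column "Number and Percentage of Participants, Number of Events", and that column is marked for all nine safety rows.

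**Part A/B SAP, laboratory results (6.3.3).** For values outside the normal range: "The results that are outside the reference ranges will be flagged in the data listings". The count for Cohort 2 is a different one: "The number and percentage who had any abnormal result based on toxicity grades in hematology, serum chemistry, or coagulation measurements". The shift table also uses toxicity grades. Observed values and changes from baseline are summarised by visit and arm.

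**Grading scale (protocol Appendix 2, Table 14 notes).** "Grade 1 will not be used for hematology values due to the large overlap with normal values at the central laboratory".

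**Both SAPs, AEs (6.3.1 and 6.3.1.2).** A subject with repeat occurrences of the same AE is counted once, and frequency counts are defined as "ie, number and percentage of subjects with an event".

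**Precedence and declared changes.** Section 1 of each SAP says: "If the methods in this SAP differ from the methods described in the protocol, the SAP will prevail". Section 7 of the Part A/B SAP has two rows, both about antibody quantification limits. Section 7 of the Part C SAP declares no change.

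**The concern.** A toxicity-grade count and a normal-range count answer different questions. With haematology Grade 1 unused, the grade-based count starts at Grade 2. Mild out-of-range blood counts then have no participant rate by arm, for an endpoint that the protocol ranks as primary. Safety laboratory tests are done in Part A only, and after baseline only in Cohort 2, so no other part of the study can supply the missing rate.

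For adverse events, SAEs and MAAEs are followed through the whole study period. A count of participants cannot distinguish one event from several of the same kind in one person. The protocol planned to show both.

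Because each SAP prevails where it differs, a reader who relies on the protocol would expect two tabulations that the governing document does not specify, and would find no statement that they were dropped.

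**Working it through.** The check is mainly a comparison of texts. The one nearby figure is protocol Table 7. Its lowest detectable rates follow from 1 − 0.05^(1/n): 2.951%, 1.487% and 0.746% for n = 100, 200 and 400, against the stated 2.95, 1.49 and 0.75. Table 7 concerns participants with an AE, so it does not depend on event counts and is not affected.

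**1. What the laboratory count loses.** I assume that the SAP's toxicity grades are those of Table 14, since protocol 3.4.8.9 sends the reader there and the SAP names no other scale.

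- Appendix 2 says that a laboratory value is graded only if it lies outside the laboratory's normal values. Dropping Grade 1 therefore removes from the count only results that are out of range.
- The bands concerned include lymphocytes 750–1,000, neutrophils 1,500–2,000, platelets 125,000–140,000 and raised white cells 10,800–15,000 per mm³.
- Take a platelet count of 130,000, if the laboratory's lower limit lies above it. The protocol's table counts it as low. In the SAP it has no grade, so it is absent from both the abnormality count and the grade-shift table. At 120,000 it would be Grade 2 and counted.
- Table 14 grades platelets only for a decrease. A high platelet count is never graded, but the protocol's table would count it as above range. The same holds for high haemoglobin.
- The reason given for dropping Grade 1 is that the bands overlap normal values. A count defined by the normal range has no such overlap.

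**2. Extent.** Cohort 2 has 3 arms × 100 = 300 planned participants and two post-baseline laboratory visits: 300 × 2 = 600 planned participant-visits.

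**3. What the AE count loses.** The event rate per person is not in the documents. As an illustration only, assume Poisson events with mean λ per person and 200 participants, the planned size of a Part A dose group. Participants with an event = 200(1 − e^−λ); events = 200λ.

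| λ | Participants | Events | Difference |
|---|---|---|---|
| 0.1 | 19.0 | 20.0 | 1.0 |
| 0.3 | 51.8 | 60.0 | 8.2 |
| 0.5 | 78.7 | 100.0 | 21.3 |
| 1.0 | 126.4 | 200.0 | 73.6 |

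The gap is negligible for rare events and grows with frequency. It refers to a row for any event. Repeats under different preferred terms still show in their own rows, so the loss across all tables is smaller than the last column.

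**4. Declaration.** Section 7 of the Part A/B SAP records changes as fine as the wording of a quantification limit, but has no safety row. Protocol section 4 requires even changes to secondary or exploratory analyses to be listed in the SAP or CSR with an explanation.

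**The case against.** **The values are tabulated.** A reader might infer that mild haematology changes appear in no table. That is not so: every Cohort 2 haematology value enters the summaries of observed value and change from baseline. Suppose the share of low lymphocyte values rose from 2.5% to 10% by a shift of a whole normal distribution. The shift is 1.960 − 1.282 = 0.68 SD. With 100 per arm the standard error of the difference is √(2/100) = 0.141 SD, so the shift is 0.68/0.141 = 4.8 standard errors and the summaries would show it. This stands for a general shift. A change confined to a few participants moves the mean little, and no such summary gives the proportion affected.

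**The graded count follows the protocol.** Section 3.4.8.9 places the abnormality criteria in Appendix 2, and leaving out haematology Grade 1 is the protocol's choice, not the SAP's. Clinically significant results are also recorded as AEs. This stands: the endpoint is not left untabulated. But the protocol promised the normal-range count as well, and the SAP does not keep it.

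**Silence is not a difference.** The SAPs supplement protocol section 4, and the table shells they mention are not among the documents, so an event column there cannot be excluded. Counting a subject once is also the ordinary rule for a participant numerator. That limits certainty. Still, the SAP texts define the counts as subjects and name no event count.

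**Repeat events.** A reader might infer that all repeat events vanish from the tables. Solicited reactions do not: Part A tabulates them by injection, and both SAPs tabulate them by day and by number of days reported. Individual AEs, SAEs and MAAEs are listed.

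**Scope.** The laboratory point cannot extend to Part C, which has no safety laboratory tests. Vital signs, named in the same protocol sentence, receive grade-shift tables at each visit.

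**Conclusion.** The point holds as a reporting gap that should be closed. The Part A/B SAP specifies no by-arm count of Cohort 2 participants outside the normal range, and its substitute cannot count out-of-range haematology values in the Grade 1 bands or in ungraded directions. Both SAPs specify participant counts without event counts; the loss mainly concerns repeat unsolicited AEs, SAEs and MAAEs. Neither departure is declared.

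Its size is modest. There is no hypothesis test, the underlying data are collected, and out-of-range laboratory values remain in continuous summaries and listings. It is tempting to put a figure on the share of participants missed, but the documents do not support one. The central laboratory's ranges are not given, the Grade 1 bands are said to overlap them largely, and blood-count results are related to each other, so they cannot be treated as independent tests.

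The conclusion assumes that Table 14 is the scale behind SAP 6.3.3 and that the unseen table shells do not add what the SAP text omits.

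**What to change.** - **Part A/B SAP 6.3.3:** restore the protocol's table, giving the number and percentage of Cohort 2 participants below and above the laboratory normal range at Day 29 and Day 57, by test and arm. Part A is complete and its reports are final, so supply the table with the end-of-study CSR, which protocol 6.4 bases on data from Day 0 onward. SAP 6.6.5 limits the final analysis to data from the start of Part B, so the table should be named there as an addition.
- **Both SAPs, AE tables:** add a number-of-events column beside the participant count, as in protocol Table 8.
- **Section 7 of both SAPs:** list any of these departures that is kept, with the reason.

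The cost is one table and one column, from data already held and, for the laboratory results, already flagged in listings. The out-of-range counts will include trivial deviations and should be read against the placebo arm.
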